### **Unlisted (Unexpected) AE/Reference Safety Information**

An AE is considered unlisted if the nature or severity is not consistent with the applicable product reference safety information. For the Ad26/protein preF RSV vaccine, the expectedness of an AE will be determined by whether or not it is listed in the IB ([IB Ad26/protein preF RSV vaccine 2021](#)).

#### **10.2.2. Attribution Definitions**

##### **Assessment of Causality**

The causal relationship to study vaccine is determined by the investigator. The following selection should be used to assess all AEs.

##### **Related**

There is a reasonable causal relationship between study vaccine administration and the AE.

##### **Not Related**

There is not a reasonable causal relationship between study vaccine administration and the AE.

The term "reasonable causal relationship" means there is evidence to support a causal relationship.

By definition, all solicited AEs at the injection site (local) will be considered related to the study vaccine administration.

#### **10.2.3. Severity Criteria**

All AEs will be coded for severity using a modified version of the FDA grading table, based on version of September 2007 ([FDA 2007](#)), included in [Appendix 4](#), Toxicity Grading Scale.

For AEs not identified in the grading table, the following guidelines will be applied:

Grade 1	Mild	Symptoms causing no or minimal interference with usual social and functional activities
Grade 2	Moderate	Symptoms causing greater than minimal interference with usual social and functional activities
Grade 3	Severe	Symptoms causing inability to perform usual social and functional activities and requiring medical intervention
Grade 4	Potentially life-threatening	Symptoms causing inability to perform basic self-care functions OR medical or operative intervention indicated to prevent permanent impairment, persistent disability OR emergency room visit or hospitalization

The severity of solicited signs and symptoms will be graded in the participant diary by the participant based on the severity assessment provided in the participant diary and then verified by the investigator using the toxicity grading scale in [Appendix 4](#). (Note: severity of the measured events will be derived from the diameter [for erythema and swelling] and the temperature measurements [for fever])

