#### **Solicited AEs**

Solicited AEs are used to assess the reactogenicity of the study vaccine and are predefined local (injection site) and systemic events for which the participant is specifically questioned and which are noted by participants in their participant diary.

After vaccination, participants will remain under observation at the study site for at least 15 minutes for presence of any acute reactions and solicited events.

In addition, participants will record solicited signs and symptoms in a participant diary for 7 days post-vaccination. All participants will be provided with a participant diary and instructions on how to complete the participant diary (see Overview in Section 8). If a paper diary is used for this study, the study staff will transcribe the information provided by the participant into the relevant sections of the eCRF. If an ediary is used, diary information will be transferred to the sponsor. After review and verbal discussion of the initial diary entries with the participant, the investigator will complete their own assessment in the relevant sections of the eCRF. Once a solicited sign or symptom from a participant diary is considered to be of severity Grade 1 or above, it will be recorded as a solicited AE.

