### A: Tables for Clinical Abnormalities

Local Reaction to Injectable Product	Mild (Grade 1)	Moderate (Grade 2)	Severe (Grade 3)	Potentially Life Threatening (Grade 4)
Pain/Tenderness #	Aware of symptoms but easily tolerated; Does not interfere with activity; Discomfort only to touch	Notable symptoms; Requires modification in activity or use of medications; Discomfort with movement	Incapacitating symptoms; Inability to do work, school, or usual activities; Use of narcotic pain reliever	Hospitalization; Pain/tenderness causing inability to perform basic self-care function
Erythema #	25 – 50 mm	51 – 100 mm	> 100 mm	Hospitalization; Necrosis or exfoliative dermatitis
Swelling #	25 – 50 mm	51 – 100 mm	> 100 mm	Hospitalization; Necrosis

# Revised by the sponsor.

Vital Signs *	Mild (Grade 1)	Moderate (Grade 2)	Severe (Grade 3)	Potentially Life Threatening (Grade 4)
Fever (°C) ** (°F)**	38.0 - 38.4 100.4 - 101.1	38.5 - 38.9 101.2 - 102.0	39.0 - 40.0 102.1 - 104.0	> 40 > 104.0
Tachycardia - beats per minute	101 – 115	116 – 130	> 130	Hospitalization for arrhythmia #
Bradycardia - beats per minute***	50 – 54	45 – 49	< 45	Hospitalization for arrhythmia #
Hypertension (systolic) - mm Hg	141 – 150	151 – 160 #	> 160 #	Hospitalization for malignant hypertension #
Hypertension (diastolic) - mm Hg	91 – 95	96 – 100	> 100	Hospitalization for malignant hypertension #
Hypotension (systolic) – mm Hg	85 – 89	80 – 84	< 80	Hospitalization for hypotensive shock #
Respiratory Rate – breaths per minute	17 – 20	21 – 25	> 25	Intubation

\* Participant should be at rest for all vital sign measurements.

\*\* For oral temperature: no recent hot or cold beverages or smoking.

\*\*\* When resting heart rate is between 60 – 100 beats per minute. Use clinical judgment when characterizing bradycardia among some healthy participant populations, for example, conditioned athletes.

# Revised by the sponsor.

Systemic (General)	Mild (Grade 1)	Moderate (Grade 2)	Severe (Grade 3)	Potentially Life Threatening (Grade 4)
Vomiting #	No interference with activity or 1 – 2 episodes/24 hours	Some interference with activity or > 2 episodes/24 hours	Prevents daily activity, requires outpatient IV hydration	Hospitalization; Hypotensive shock

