#### **5.5.1.2. Analysis of Adverse Events**

Number and percentage of participants with at least one particular AE (unsolicited/solicited) will be tabulated. Unsolicited AEs will be summarized by System Organ Class and Preferred Term.

Solicited AEs will be summarized by class (administration site, systemic) and preferred term. AESI analyses will be summarized by Interest Category and Preferred Term.

For solicited AEs, the following tables will be provided: summary, by worst severity grade, at least grade 3, related (systemic only), time to onset (in days) and duration (in days). Note: Duration is defined as number of days from the start of the event until resolution of the event. The time to first onset is defined as (date of first onset – reference date + 1). The reference date is the start date of the post-dose period.

For unsolicited AEs following tables will be provided: summary table (including SAE, fatal outcome, potential AESI, AE leading to study discontinuation), all events, most frequent, at least grade 3, related, AE leading to study discontinuation, SAE, related SAE, potential AESIs qualified for assessment and potential AESI.

Moreover, table with Covid-19 related AEs, potential AESI as identified by the investigator, potential AESIs selected programmatically and potential AESI qualified for assessment will be created.

Potential AESIs selected programmatically will be tabulated by categories: '*Embolic and thrombotic events (SMQ)*' and '*Haematopoietic Thrombocytopenias (SMQ) (broad) or HLT = Thrombocytopenias*'. Potential AESI determined programmatically, related to study vaccine (investigator assessment), will be tabulated similarly.

Potential AESIs as identified by the investigator, will be tabulated by categories: '*Embolic and thrombotic events (SMQ)*' and '*Haematopoietic Thrombocytopenias (SMQ) (broad) or HLT = Thrombocytopenias*', and '*Other*'. Potential AESI as identified by the investigator, related to study vaccine (investigator assessment), will be tabulated similarly.

Potential AESIs qualified for assessment will be tabulated by categories: '*Embolic and thrombotic events (SMQ)*' and '*Haematopoietic Thrombocytopenia (SMQ) (broad) or HLT=Thrombocytopenias*'.

All AESI analyses will be presented by phase as well as by time interval. The definition of the different time intervals can be found in Section [5.1.2](#).

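### The diameter rule for erythema and swelling severity cannot return Appendix 4's Grade 4, and no text says which grade prevails when a Grade 4 criterion is met

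*Protocol*

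**What the plan says.** Protocol Section 10.2.3 sets Appendix 4 as the severity scale for all AEs. For solicited events the participant grades in the diary, and the grade is "then verified by the investigator using the toxicity grading scale in" Appendix 4. A bracketed Note then treats the measured events separately: "severity of the measured events will be derived from the diameter [for erythema and swelling", with fever graded from the temperature.

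Table A of Appendix 4 (Protocol Section 10.4) grades erythema and swelling by size for Grades 1 to 3. Grade 4 carries no size. For erythema it reads "Hospitalization; Necrosis or exfoliative dermatitis"; for swelling it reads "Hospitalization; Necrosis".

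Protocol Section 8.3.2 (Solicited AEs) says that after diary review "the investigator will complete their own assessment in the relevant sections of the eCRF". It also sets the recording threshold: a diary sign is entered when it is "considered to be of severity Grade 1 or above, it will be recorded as a solicited AE".

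SAP Section 5.5.1.1 draws the tabulated solicited AEs from the investigator's assessment pages (the CE domain), classifies severity as Grades 1 to 4 and leaves Grade 0 solicited events out. SAP Section 5.5.1.2 plans solicited-AE tables "by worst severity grade, at least grade 3", among others.

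**The concern.** For erythema and swelling, two instructions in the same paragraph give different grades for the same lesion whenever a Grade 4 criterion is met. Someone who follows the Note grades by ruler and stops at Grade 3. Someone who follows the verification sentence uses the whole Appendix 4 row and reaches Grade 4. The investigator who completes the CE page is bound by both.

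At stake are the worst-grade and Grade 3 or higher rows of the solicited local table. Comparing the reactogenicity of the two materials is a secondary objective, and these rows show its severe end. If sites or programmers resolve the conflict differently, a necrotic reaction could be shown as mild in the solicited table while another record in the same report describes necrosis or a hospitalization.

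**Working it through.** The plan has no figure to reproduce here. The check sets the rule against the scale.

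**1. Grade from diameter alone** (bands from Appendix 4, same for erythema and swelling):

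| Diameter | Derived grade | Appendix 4 grade if necrosis is present |
|---|---|---|
| below 25 mm | 0 (no grade) | 4 |
| 25–50 mm | 1 | 4 |
| 51–100 mm | 2 | 4 |
| above 100 mm | 3 | 4 |

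Evaluated at every whole millimetre from 0 to 1000, the derived grade has a maximum of 3. Fever, covered by the same Note, has no such gap: its Grade 4 is a temperature above 40 °C.

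**2. Effect on the planned tables, if the derived grade is the one entered on the CE page:**

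- Above 100 mm: the participant stays in the Grade 3 or higher table, but the worst grade is shown as 3, not 4.
- 25 to 100 mm: the participant is shown at Grade 1 or 2 and is absent from the Grade 3 or higher table for that event.
- Below 25 mm: the Grade 1 threshold in Protocol Section 8.3.2 is not met, so there is no solicited erythema or swelling AE, and SAP Section 5.5.1.1 omits Grade 0.

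**3. What still captures the event.** Protocol Section 10.2.5 requires all AEs to be recorded whatever their severity, and any hospitalization for an event to be reported as an SAE, with exceptions that do not concern an acute local reaction. Necrosis and exfoliative dermatitis are not among the diary terms, so under Section 8.3.2 they fall to unsolicited AEs. One attribute can differ: Section 10.2.2 makes solicited injection-site AEs related by definition, whereas for an unsolicited AE relatedness is the investigator's opinion.

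**4. Size of one misgraded case.** With 120 per group (Protocol Table 2), one participant is 1/120 = 0.83%. Exact two-sided 95% limits (Clopper-Pearson):

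- 1/120: lower limit 1 − 0.975^(1/120) = 0.02%; upper limit is the p that solves (1 − p)^120 + 120p(1 − p)^119 = 0.025, which is 4.56%.
- 0/120: upper limit 1 − 0.025^(1/120) = 3.03%.

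Moving one participant out of the Grade 3 or higher row thus changes 0.83% (0.02% to 4.56%) to 0% (0% to 3.03%). The plan does not call for intervals on AE percentages; these only show scale.

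**5. How the SAP treats the same problem elsewhere.** For vital signs, SAP Appendix 6 grades from values only and merges Grades 3 and 4, because Grade 4 needs clinical interpretation. Grade 4 erythema and swelling are equally clinical, yet no corresponding rule is written for them.

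**The case against.** The best defence is that the Note only supplies a starting grade. It follows the verification sentence in brackets and can be read to mean that participants should not grade a measured sign subjectively. The investigator then verifies against all of Appendix 4 and completes a separate assessment. SAP Sections 5.5.1.1, 5.5.1.3 and 5.5.1.4 all base the solicited analysis on that assessment. Where the SAP wants grading from values alone, it says so, and it does so only for vital signs.

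This defeats three stronger readings that a reader might infer:

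- That Grade 4 erythema or swelling can never appear in the tables. The cap is certain for the derived grade. The documents do not establish it for the analysed grade, which is the investigator's.
- That a necrotic reaction below 25 mm would not be an AE at all. It would have no solicited erythema or swelling record under the Note, but it must still be recorded as an unsolicited AE or SAE.
- That exfoliative dermatitis defines Grade 4 for both signs. Appendix 4 lists it for erythema only.

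The defence does not remove the conflict. The Note is worded as a flat rule, and a specific rule is commonly taken to override a general one. It governs the investigator's assessment as well. The harmonious reading is available, but it is not written down.

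**Conclusion.** The point holds as a conflict between a stated rule and the scale it should apply. Followed literally, the Note cannot return a grade that the same section adopts for all AEs, and no text says whether the diameter or the investigator's Appendix 4 grade prevails.

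The impact is minor. It arises only if a reaction meets a Grade 4 criterion, and it matters only if the CE page then carries the diameter grade. The documents give no frequency for such reactions. That they are rare is an assumption, consistent with Protocol Section 2.3.1, which describes the commonest local reactions, swelling included, as mild to moderate; the number in this trial may be zero. Safety is analysed descriptively without formal comparison of the groups. The primary endpoint, the Day 15 pre-F ELISA titer, is unaffected.

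**What to change.** Reconcile Protocol Section 10.2.3, Appendix 4 and SAP Section 5.5.1.1:

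- Limit the Note to Grades 1 to 3 for erythema and swelling.
- Add that, when the investigator records a Grade 4 criterion already listed in Appendix 4 for that sign, the event is Grade 4 and is recorded as a solicited AE whatever its diameter.
- State in the SAP that this grade is the one held in the CE record and used in the solicited-AE tables.

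The cost is one sentence in the protocol, one in the SAP and one programming check. No visit or procedure is added, and the criteria themselves do not change. The investigator already completes an assessment of solicited events; the one thing to confirm is that the CE page lets Grade 4 be entered independently of the measured diameter.

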#### **10.2.4. Special Reporting Situations**

Safety events of interest for a sponsor study vaccine in an interventional study that may require expedited reporting or safety evaluation include, but are not limited to:

- Overdose of a sponsor study vaccine
- Suspected abuse/misuse of a sponsor study vaccine
- Accidental or occupational exposure to a sponsor study vaccine
- Medication error, intercepted medication error, or potential medication error involving a Johnson & Johnson medicinal product (with or without patient exposure to the Johnson & Johnson medicinal product, eg, product name confusion, product label confusion, intercepted prescribing or dispensing errors)
- Exposure to a sponsor study vaccine from breastfeeding
- Reporting of participant pregnancy or participant partner(s) pregnancy

Special reporting situations should be recorded in the eCRF. Any special reporting situation that meets the criteria of an SAE should be recorded on the SAE page of the eCRF.

#### **10.2.5. Procedures**

##### **All AEs**

All AEs, regardless of seriousness, severity, or presumed relationship to study vaccine, must be recorded using medical terminology in the source document and the eCRF. Whenever possible, diagnoses should be given when signs and symptoms are due to a common etiology (eg, cough, runny nose, sneezing, sore throat, and head congestion should be reported as “upper respiratory infection”). Investigators must record in the eCRF their opinion concerning the relationship of the

AE to study vaccine. All measures required for AE management must be recorded in the source document and reported according to sponsor instructions.

For all studies with an outpatient phase, including open-label studies, the participant must be provided with a "wallet (study) card" and instructed to carry this card with them for the duration of the study indicating the following:

- Study number
- Statement, in the local language(s), that the participant is participating in a clinical study
- Investigator's name and 24-hour contact telephone number
- Local sponsor's name and 24-hour contact telephone number (for medical personnel only)
- Site number
- Participant number
- Any other information that is required to do an emergency breaking of the blind

### **SAEs**

All SAEs that have not resolved by the end of the study, or that have not resolved upon the participant's discontinuation from the study, must be followed until any of the following occurs:

- The event resolves
- The event stabilizes
- The event returns to baseline, if a baseline value/status is available
- The event can be attributed to agents other than the study vaccine or to factors unrelated to study conduct
- It becomes unlikely that any additional information can be obtained (participant or health care practitioner refusal to provide additional information, lost to follow-up after demonstration of due diligence with follow-up efforts)

Any event requiring hospitalization (or prolongation of hospitalization) that occurs during participation in the study must be reported as an SAE, except hospitalizations for the following:

- Hospitalizations not intended to treat an acute illness or AE (eg, social reasons such as pending placement in long-term care facility).
- Surgery or procedure planned before entry into the study (must be documented in the eCRF). Note: Hospitalizations that were planned before the signing of the ICF, and where the underlying condition for which the hospitalization was planned has not worsened, will not be considered SAEs. Any AE that results in a prolongation of the originally planned hospitalization is to be reported as a new SAE.

The cause of death of a participant in a study during the entire study period, whether or not the event is expected or associated with the study vaccine, is considered an SAE and must be reported.

Information regarding SAEs will be transmitted to the sponsor using an SAE reporting form and safety report form of the eCRF, which must be completed and reviewed by a physician from the study site, and transmitted in a secure manner to the sponsor within 24 hours. The initial and follow-up reports of an SAE should be transmitted in a secure manner electronically or by facsimile (fax). Telephone reporting should be the exception and the reporter should be asked to complete the appropriate form(s) first.

### **Adverse Events of Special Interest**

AESIs, including potential AESIs, will be carefully monitored during the study by the sponsor and must be reported to the sponsor within 24 hours of awareness irrespective of seriousness (ie, serious and nonserious AEs) or causality assessment, following the procedure described above for SAEs and will require enhanced data collection.

## **10.2.6. PQC Handling**

### **Definition**

A PQC is defined as any suspicion of a product defect related to manufacturing, labeling, or packaging, ie, any dissatisfaction relative to the identity, quality, durability, reliability, or performance of a distributed product, including its labeling, drug delivery system, or package integrity. A PQC may have an impact on the safety and efficacy of the product. In addition, it includes any technical complaints, defined as any complaint that indicates a potential quality issue during manufacturing, packaging, release testing, stability monitoring, dose preparation, storage or distribution of the product or the drug delivery system.

All complaints related to ANY part of the Ad26/protein preF RSV vaccine must be reported within 1 business day. In the event of public holiday, measures must be taken to ensure reporting no later than calendar day 3.

### **Procedures**

All initial PQCs must be reported to the sponsor by the study-site personnel within 24 hours after being made aware of the event.

A sample of the suspected product should be maintained under the correct storage conditions until a shipment request is received from the sponsor.

## **10.2.7. Contacting Sponsor Regarding Safety, Including Product Quality**

The names (and corresponding telephone numbers) of the individuals who should be contacted regarding safety issues, PQCs, or questions regarding the study are listed in the Contact Information page(s), which will be provided as a separate document.

## **10.3. Appendix 3: Regulatory, Ethical, and Study Oversight Considerations**

### **10.3.1. Regulatory and Ethical Considerations**

#### **Investigator Responsibilities**

The investigator is responsible for ensuring that the study is performed in accordance with the protocol, current ICH guidelines on Good Clinical Practice (GCP), and applicable regulatory and country-specific requirements.

GCP is an international ethical and scientific quality standard for designing, conducting, recording, and reporting studies that involve the participation of human participants. Compliance with this standard provides public assurance that the rights, safety, and well-being of study participants are protected, consistent with the principles that originated in the Declaration of Helsinki, and that the study data are credible.

#### **Protocol Clarification Communications**

If text within a final approved protocol requires clarification (eg, current wording is unclear or ambiguous) that does not change any aspect of the current study conduct, a protocol clarification communication (PCC) may be prepared. The PCC Document will be communicated to the Investigational Site, Site Monitors, Local Trial Managers (LTMs), Clinical Trial Managers (CTMs), and/or Contract Research Organizations (CROs) who will ensure that the PCC explanations are followed by the investigators.

The PCC Document may be shared by the sites with Independent Ethics Committees/Institutional Review Boards (IECs/IRBs) per local regulations.

The PCC Documents must NOT be used in place of protocol amendments, but the content of the PCC Document must be included in any future protocol amendments.

